8.2.2.3 Completion of the 4-month Follow-Up Woman Form

In case of live birth and four months after the delivery, the woman will receive an e-mail asking to re-access the website.

- Access the website and re-enter the unique file number provided by e-mail at the time of the Pregnancy and Outcome Forms submission

* Ideally the HCP in charge of the pregnancy follow-up (for e.g. midwife, obstetrician,...)

- Provide the age, height and weight of the baby
- Provide any congenital anomaly detected since birth, if applicable
- Collect late development detected since birth, if applicable

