8 STUDY PROCEDURES AND SCHEDULE

8.1 Overview of safety data

Pregnancy information

Date of diagnosis, date of LMP, date and results of ultrasound (if applicable) and expected delivery date.

Exposure to ella®

Data on exposure to ella® include date of ella® intake and number of tablets taken, time from intercourse to ella® intake; pregnancy stage at ella® exposure, pregnancy status before ella® intake.

Outcomes

All outcomes and the data collected to assess them are:

- Live birth – gender, birth weight, gestational age, delivery method and Apgar scores will be collected in all cases. For healthy babies and those with congenital anomalies or other neonatal diagnosis, the study observation period will last until 4 months after delivery;
 - Congenital anomaly or other neonatal diagnosis – description of anomaly and possible causes will be additionally collected;
 - Neonatal death (from birth through to 28 completed days of age*) – age at death, possible etiology and result of autopsy if performed will be additionally collected.
- Pregnancy loss – gestational age, possible etiology of pregnancy loss and any complications (vaginal bleeding, need for curettage, infection) will be collected in all cases.
 - Spontaneous abortion (or early fetal death i.e. < 20 completed weeks of gestation*)
 - Ectopic pregnancy
 - Induced abortion (no medical reason – woman's elective choice, elective abortion with fetal defects, or maternal health complications)
 - Stillbirth:
 - Intermediate fetal death (more than 20 completed weeks of gestation but less than 28*)
 - Late fetal death (\geq 28 completed weeks of gestation*).

Maternal health complications of pregnancy

In all cases, relationship of the outcome observed with the exposure to ella® will be assessed by the HCP and according to the standard pharmacovigilance process.

* According to the WHO International Classification of Disease (ICD)

Prior and concomitant medications

Prior and concomitant medications will be collected in the HCP or women questionnaires. Collection period covers the pregnancy duration from LMP to the end of pregnancy.

Other

Maternal family history; recreational drug use (tobacco, alcohol, illicit drugs) and serological and prenatal tests.

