8.2.1.4 Completion of the 4-month Follow-Up HCP Forms

In case of live birth and 4 months after the delivery, the HCP be reminded to re-access the website. The HCP will be asked to:

- Access the website with the HCP unique user ID and password
- Collect the age, height and weight of the baby
- Collect congenital anomaly detected since birth, if applicable
- Collect late development detected since birth, if applicable
- Collect death data, if applicable.

8.2.2 Completion of the on-line questionnaire directly by the woman:

Up to three questionnaires will be completed by the woman: the first two ones including Pregnancy and Outcome Forms, and one for live birth only, a 4-month Follow-up Form.

* In case a woman completed the questionnaire on her own, she should be reminded to bring her unique patient number to allow the HCP to provide further information on the pregnancy if requested.

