8.4 Methods of data collection

Online questionnaires for data collection will be available on a dedicated and secured website. Once submitted, these questionnaires will be received by the Sponsor's drug safety department.

Specific questionnaires may be completed on-line either by the HCP or directly by the woman at any time from pregnancy diagnosis up to known pregnancy outcome.

There will be a specific on-line questionnaire to be completed by the HCP where data on pregnancy diagnosis and exposure to ella® will first be collected. Once the pregnancy outcome is known, the HCP will be requested to complete the rest of the questionnaire.

For live birth only (except for neonatal death), HCP will be requested to complete a follow-up questionnaire 4 months after the delivery date (**4 month Follow-Up HCP Form**).

When completed directly by the woman, the woman will have to complete a simplified questionnaire where data on pregnancy diagnosis, exposure to ella®, and if known at the time of the questionnaire completion, the pregnancy outcome.

For live birth only (except for neonatal death), the woman will be encouraged to fill in a 4-month Follow-Up Form around 4 months after the delivery date (**4 month Follow-Up Woman Form**).

The on-line questionnaires together with instructions will be available in English for the HCP and in both English and Spanish for the woman.

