9.2.2.2 Primary Objective Assessments

The primary objective of this observational study is to estimate the rates of occurrence of outcomes of pregnancies exposed to ella® in order to detect a possible signal of concern for adverse outcomes related to exposure to ella®.

Each pregnancy outcome will be described by proportions (cumulative incidence/prevalence) with exact 95% confidence interval.

For each pregnancy outcome, data from all sources (past and current clinical trials, registry, spontaneous pharmacovigilance reporting) will be used. Outcomes to be evaluated are defined as follows:

All Induced abortions (due to a medical/non-medical reason):

Proportion of normal-appearing pregnancies (with analysable ultrasound results) before induced abortion = number of normal-appearing pregnancies with ultrasound compatible with normal growth and development/ number of pregnancies with analysable ultrasound results.

Therapeutic abortion (medical indication)

Proportion of therapeutic abortions = number of therapeutic abortions / number of pregnancies

Birth outcomes

Proportion of live births = number of live births/ total number of births

Proportion of healthy babies = number of live births without any anomaly (healthy babies) / number of deliveries

Total live birth prevalence of congenital anomalies = number of live births with congenital anomalies / number of live births

Proportion of neonatal deaths = number of neonatal deaths / number of live births

Congenital anomalies:

Total prevalence of congenital anomalies = total number of congenital anomalies (terminations of pregnancy for fetal anomaly (TOPFA), stillbirths, live births with congenital anomalies / total number of births (live births + stillbirths)

Pregnancy loss outcomes

Proportion of spontaneous abortions (or spontaneous abortion cumulative incidence) = number of spontaneous abortions / number of pregnancies

Proportion of intermediate fetal deaths* = number of intermediate fetal deaths / number of pregnancies

Proportion of stillbirths (or stillbirth cumulative incidence) = number of stillbirths / number of pregnancies

* more than 20 completed weeks of gestation but less than 28, according to the WHO fetal death classification.

Proportion of ectopic pregnancies (or ectopic pregnancy cumulative incidence) = number of ectopic pregnancies / number of pregnancies with known outcomes reported

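### The woman's 4-month form, as listed, has no infant-death item although the HCP form has one, so neonatal deaths may be under-counted in self-reported cases.

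*Protocol*

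**What the plan says.** Each reporter type has its own 4-month form for live births.

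- **HCP form (Protocol 8.2.1.4):** growth, late-detected anomaly, late development and, last, "Collect death data, if applicable".
- **Woman's form (Protocol 8.2.2.3):** "Provide the age, height and weight of the baby", then "Provide any congenital anomaly detected since birth, if applicable", then "Collect late development detected since birth, if applicable". The list stops there.

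Section 8.1 defines "Neonatal death (from birth through to 28 completed days of age" and requires age at death, possible etiology and any autopsy result for such cases. For other live births it says that "the study observation period will last until 4 months after delivery". Section 8.4 states who receives the woman's form: "For live birth only (except for neonatal death), the woman will be encouraged to fill in a 4-month Follow-Up Form".

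Under the primary objective, Section 9.2.2.2 defines "Proportion of neonatal deaths = number of neonatal deaths / number of live births". The definition makes no distinction by reporter type.

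**The concern.** The two lists match item for item until the last line, and the protocol gives no reason for the difference. The woman's last item even keeps the verb used for the HCP, which suggests that her list was adapted from the HCP list and lost its final line.

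A woman may submit her outcome form as soon as she knows the outcome, which can be well before day 28. The 4-month form then goes to live births not already known to be neonatal deaths. Those are the infants for whom a later death would still be unrecorded.

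If deaths are sought less thoroughly in self-reported cases, those births stay in the denominator of the neonatal death proportion while some of their deaths may not reach the numerator. That bias is downward, in an analysis whose stated purpose is to detect a signal of concern. If a death was never asked about, the analyst cannot recover it later.

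**Working it through.** No figure in the protocol bears on this point, so the check is a comparison of the two lists followed by a search for other routes.

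**1. The two 4-month forms side by side**

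| Item | HCP form (8.2.1.4) | Woman's form (8.2.2.3) |
|---|---|---|
| Website access | yes | yes |
| Age, height, weight | yes | yes |
| Anomaly found since birth | yes | yes |
| Late development | yes | yes |
| Death | yes | not listed |

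**2. Other routes by which a later death could be recorded**

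| Route | Section | Limit |
|---|---|---|
| Neonatal death is an answer on the woman's outcome form | 8.2.2.2 | Covers only deaths before she submits it |
| She can reopen her file at any time | 8.2.2.2 | Nothing prompts her to do so after a death |
| Sponsor may contact the reporter about the baby's health at 4 months | 8.3 | Optional, and mainly directed to the HCP |
| System e-mail when she has named no HCP | 8.3 | No question on death stated; the 4-month e-mail in 8.2.2.3 leads to the form without the item |
| 4-month safety contact with HCP, referent physician or woman | 14.1, item 5 | No question on death stated |

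The referent physician is optional and cannot complete the questionnaire for her (4.2.2). The repeat-contact schedule in 8.3 is for HCPs. Her e-mail address is kept from the sponsor. The weakest case is therefore the self-reporter who names no HCP.

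**3. Which estimate is affected**

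Deaths from day 29 to 4 months fall inside the observation period but enter no proportion defined in 9.2.2.2. The effect is confined to neonatal deaths that occur after the outcome form is submitted.

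**4. How the bias would scale (illustration only)**

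Let *s* be the share of live births that are self-reported, and *m* the share of neonatal deaths in those cases that no route captures. Assume the same risk of neonatal death in both reporter groups and complete capture in HCP-reported cases. Then

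observed / true proportion = 1 − *s* × *m*.

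For example, *s* = 0.50 and *m* = 0.25 give 1 − 0.125 = 0.875.

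| *s* | *m* = 0.10 | *m* = 0.25 | *m* = 0.50 | *m* = 1 |
|---|---|---|---|---|
| 0.25 | 0.975 | 0.9375 | 0.875 | 0.75 |
| 0.50 | 0.95 | 0.875 | 0.75 | 0.50 |
| 0.75 | 0.925 | 0.8125 | 0.625 | 0.25 |

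Both *s* and *m* are assumptions, since the protocol gives neither. The column *m* = 1 is a mathematical limit and not a plausible value: it would need every neonatal death in a self-reported case to be lost, including those before submission, for which the outcome form has an answer.

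**The case against.** The strongest objection is that the bullets in 8.2.2.3 are an outline and not the form. Section 4.2.2 places the content of the woman's questionnaires in a separate document submitted to the IRB, which is not shown. That stands: the item may already be there, and the fix has to allow for it. It does not remove the discrepancy in the protocol, where one list names death and its counterpart does not.

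Second, the 4-month form was not designed to find neonatal deaths. Section 8.4 excludes known neonatal deaths from it, and a footnote to the study schedule gives its purpose as finding anomalies not detected at birth. This explains the emphasis on anomalies. It does not explain why the HCP form, with the same purpose and the same exclusion, asks about death.

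Third, a reader might infer that later deaths in self-reported cases are missed outright and cannot enter the numerator. The documents do not support that. Besides the routes set out above, Section 7 lets pharmacovigilance contact the reporter for more information. A footnote to 8.2.1.3 also asks self-reporting women to bring their patient number, so that an HCP can add information. Under-counting is possible but not certain.

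A reader might also infer that bereaved women would not answer a form asking for the baby's height and weight, which would tie missing data to the outcome. That is plausible, but nothing in the protocol shows it.

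Finally, Table 3 might be used to size the problem. Going from 0 to 1 event moves its upper bound from 3.6% to 5.4% at 100 and from 0.9% to 1.4% at 400. This shows only that one event moves an exact interval, whatever the outcome. It does not measure the bias. Table 3 also counts exposed pregnancies, and the target of 400 includes losses and abortions, so 400 is not the live-birth denominator.

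**Conclusion.** The point holds in a limited form. As listed, the two 4-month forms ascertain infant death unequally by reporter type. Neonatal deaths after the woman submits her outcome form may be under-counted, chiefly where she has named no HCP and follow-up rests on a system e-mail. None of the other routes states a prompted question on death at 4 months.

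The effect is limited to the neonatal death proportion and its direction is downward. The size cannot be determined from the protocol, and the table of ratios shows only how it would depend on two unknown quantities. The conclusion assumes that the list in 8.2.2.3 reflects the form in use. If the separate questionnaire document contains a death item, what remains is an inconsistency of text.

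The correction should be made: it is cheap, it concerns an outcome analysed under the primary objective, and the missing information could not be restored at analysis.

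**What to change.** Add the HCP death item to the 4-month Follow-Up Woman Form in Section 8.2.2.3. Ask whether the infant is alive and, if not, the age at death and possible cause, in line with what Section 8.1 requires for neonatal deaths. Put the question before the growth items, so that those are skipped after a death, and word it with care.

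If the separate questionnaire document described in Section 4.2.2 already includes the item, align the list in 8.2.2.3 with it.

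The cost is one question on an online form and IRB approval of the revised questionnaire. The drawback is a sensitive question put to bereaved women, which careful wording can address.

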8.3 Participant follow-up

Reporters (HCP or women) will be asked to carefully keep either their user ID and password or the unique patient number they received.

Reporters, mainly the HCP can be contacted by the Sponsor's drug safety department to obtain medical follow-up information on women included in the study or on baby(ies)'s health 4 months after the delivery date (for live births only).

However, as stated earlier, if the reporter is a woman who did not provide contact details of an HCP the system will generate an e-mail to the woman to request further information. Note that the woman email address will be kept blinded to the sponsor.

Additionally, each HCP having enrolled a woman before the pregnancy outcome was known will be contacted by the Sponsor's drug safety department at 20 weeks of the pregnancy and at the scheduled delivery date and will be asked to complete the online questionnaire accessible on the website.

This contact will be done via e-mail within 15 days after the presumed date of delivery. If no answer is received within 30 days, the HCP will be contacted again twice with 1 month interval.

8.4 Methods of data collection

Online questionnaires for data collection will be available on a dedicated and secured website. Once submitted, these questionnaires will be received by the Sponsor's drug safety department.

Specific questionnaires may be completed on-line either by the HCP or directly by the woman at any time from pregnancy diagnosis up to known pregnancy outcome.

There will be a specific on-line questionnaire to be completed by the HCP where data on pregnancy diagnosis and exposure to ella® will first be collected. Once the pregnancy outcome is known, the HCP will be requested to complete the rest of the questionnaire.

For live birth only (except for neonatal death), HCP will be requested to complete a follow-up questionnaire 4 months after the delivery date (**4 month Follow-Up HCP Form**).

When completed directly by the woman, the woman will have to complete a simplified questionnaire where data on pregnancy diagnosis, exposure to ella®, and if known at the time of the questionnaire completion, the pregnancy outcome.

For live birth only (except for neonatal death), the woman will be encouraged to fill in a 4-month Follow-Up Form around 4 months after the delivery date (**4 month Follow-Up Woman Form**).

The on-line questionnaires together with instructions will be available in English for the HCP and in both English and Spanish for the woman.

9 STATISTICAL PROCEDURES

9.1 Sample size justification

As described below, a sample size of 400 pregnancies with known outcomes was chosen as it provides 80% power to detect a two-fold increase (Risk Ratio=2) for events with a proportion of 3% and a three-fold increase (RR=3) for events with a proportion of 1% (e.g., approximately equivalent to the total prevalence of congenital heart defects) (refer to Annex 1).

Sample size and confidence interval calculations were done using Stata (version 11, Statacorp) and EpiInfo (CDC, Atlanta, GA) software programs.

Estimates for sample size requirements were performed with the goal of detecting a signal, if one exists, of an increase in the proportion of adverse pregnancy outcomes for pregnancies exposed to ella® compared to a given reference population. For these calculations, it is assumed that event rates / proportions would be comparable for an unexposed population and its corresponding source population, as by far most (essentially all) pregnancies in the source population would be unexposed to ella®.

Sample size calculations were performed assuming a type-I (alpha) error rate of 0.05, two-sided tests and a ratio of exposed to unexposed group of 1:10. Higher ratios (e.g., 1:6 or 1:4) would require somewhat higher sample sizes for the exposed group (detailed calculations are not shown) but the difference would be relatively small as the main determinant of study power will be the number of pregnancies exposed to ella®.

Pregnancies exposed to ella® will come from various population sources. In this context, stratified analyses for country-specific (or regional) outcomes may be helpful but would pose substantial limits as to the power for detecting the statistical significance of any observed differences.

Various sources of data may be found for large numbers of (essentially all) unexposed pregnancies for different adverse pregnancy outcomes (e.g. for congenital anomalies, population-based data from registries for congenital anomalies, notably members of the European Surveillance of Congenital Anomalies, EUROCAT).

The term proportion is being used here as the measure of the frequency of adverse outcomes (e.g., preterm delivery / intrauterine growth restriction) and/or a specific adverse event (e.g., stillbirths, congenital anomalies). This may represent a cumulative incidence or in case of congenital anomalies the total or live birth prevalence of an anomaly (prevalence is the accepted term in the field of congenital anomalies to take into account early / unrecognized pregnancy loss, which precludes a true calculation of an incidence rate for congenital anomalies in the general population).

Table 1 (Annex 1) presents the sample size requirements for comparisons of proportions of adverse outcomes in pregnancies exposed to ella® versus those in the general population (essentially all unexposed). In summary, a sample size of approximately 50 and 100 pregnancies exposed to ella® can provide sufficient power to detect a two-fold increase [Risk Ratio (RR) = 2] in the risk of an adverse event with a baseline frequency of 20 (such as miscarriage) and 10%, respectively [such as intrauterine growth restriction as defined at birth (i.e. Small for Gestational Age)]; for a 50% increase (RR=1.5), the corresponding sample sizes would be approximately 160 and 375, respectively. A sample size of approximately 200 would provide a power of 80% to detect a two-fold increase for an adverse pregnancy event with a proportion of 5% in the general population (such as preterm birth). A sample size of approximately 400 would provide 80% power to detect a two-fold increase (RR=2) for events with a proportion of 3% and a three-fold increase (RR=3) for events with a proportion of 1% (e.g., approximately equivalent to the total prevalence of congenital heart defects ^{[1],[2],[3]}). For rarer events (e.g., those noted in Table 2 – Eurocat data) with a proportion of 0.1% (e.g., oro-facial clefts with a

prevalence of approximately 1 per 1000) or 0.05% (e.g., major specific congenital anomalies such as spina bifida which has a baseline total prevalence of about 4-5 per 10,000), sufficient power to detect even a ten-fold increase (RR=10) would require, respectively, almost 500 and 1000 pregnancies exposed to ella®; detection of a three-fold increase (RR=3) would require approximately 4000 pregnancies exposed to ella® and 40,000 unexposed pregnancies.

Confidence intervals are also provided for proportions of adverse outcomes that may be obtained for a given number of pregnancies exposed to ella® (Table 3, Annex 1). These confidence intervals will be used to evaluate the precision of estimates for assessing the frequency of various adverse pregnancy outcomes in the pregnancies exposed to ella®.

In addition, for sample sizes of 50, 100, 400 and 1000, one-sided 97.5% binomial exact confidence intervals were calculated for the proportion of adverse outcomes assuming that zero adverse events are observed for a given sample. The upper bounds of these confidence intervals (the lower bound is fixed at zero) can be used as an approximate indication of what may be the highest event rates that would be missed because of a limited sample size. In particular, these confidence intervals can be used to assess to what extent rare outcomes (e.g., specific congenital anomalies) may be missed given the (highest) sample sizes that may be feasible to collect.

In summary, sample size calculations described above and presented in detail in Table 1 (Annex 1) show that for relatively frequent events, e.g., spontaneous abortions, or a composite index of different adverse outcomes (e.g., intrauterine growth retardation, preterm delivery and congenital anomalies) with a baseline proportion of 20% and 10%, sample sizes of 50 and 100, respectively, can provide sufficient power to detect a two-fold increase in the risk of adverse events associated with exposure to ella®. For events with a baseline proportion of 5 and 3% in the population, the corresponding sample sizes would be 200 and 400, respectively. For rare outcomes such as specific congenital anomalies (Table 2, Annex 1), only very high increases in the risk (Table 1, Annex 1) may be detectable given feasibility considerations.

Taking into account the above calculations and feasibility considerations, a sample size of 400 pregnancy outcomes was chosen for the study.

